4.12 Duration of Therapy

- Within 4 weeks of enrollment, patients will be biopsied (optional) and fiducial markers placed, if applicable.
- Within 2 weeks of fiducial marker placement, if applicable, patients will be randomized.
- LHRH agonist or antagonist androgen deprivation therapy (ADT): LHRH agonist therapy may start up to two months prior to signing consent form or any time after signing consent form, up to two weeks after fiducial marker placement in men with intermediate or high risk prostate cancer (optional). Intermediate risk patients or high risk patients may receive 4-6 (+/- 2 months) months LHRH agonist therapy.
- Anti-androgen therapy: bicalutamide or flutamide will be administered in those planned to have LHRH agonist ADT 1-14 days prior to LHRH agonist therapy. Anti-androgen should be continued for 2-4 months (\pm 2 months), liver function tests or side effects permitting.
- Arm I: SIMRT will begin within 6 weeks of fiducial marker placement, if applicable. The therapy will consist of 40 fractions over 8 weeks.
- Arm II: HTIMRT will begin within 6 weeks of fiducial marker placement, if applicable. The therapy will consist of 38 fractions over 7.5 weeks.
- Treatment should be stopped for grade 4 acute toxicity (according to the current version of Common Terminology Criteria for Adverse Events (CTCAE version 4), but may be resumed per protocol if the treatment break is less than 10 working days. Since we have never observed grade 4 toxicity acutely using IMRT, such an event is unlikely. If grade 4 toxicity resolves beyond the 10 days the treating physician will decide whether to give additional RT.
- Treatment will be stopped if metastasis is detected by radiographic or pathologic evidence and the patient will be removed from the study, but not from the intent-to-treat analysis. A work-up for metastasis during treatment will only be carried out if the treating physician deems necessary.
- Prostate biopsies will be taken at 2-2.5 years post completion of all therapy (referred to as 2 yr post-treatment protocol biopsies). These are research biopsies that are not typically done, but which have been shown to be of predictive value in our studies (29) and those of others.

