9.1 Definitions

- *Biopsy failure rate*: The proportion of positive biopsy findings among patients without clinical or biochemical failure 2-2.5 years after completing study treatment (RT or ADT, whichever is longer).
- *Two-year failure rate*: The proportion of patients with either (i) biopsy failure 2-2.5 year after completing treatment (RT or ADT, whichever is longer) or (ii) evidence of biochemical and/or clinical failure (local, regional or distant failure) at any time prior to the planned 2 year post treatment biopsy.
- *Acute toxicity*: toxicity occurring during treatment and within three months of completing treatment
- *Late toxicity*: toxicity occurring more than three months after treatment completion.
- *Failure rate*: The cumulative incidence of biochemical or clinical failure allowing for competing risk as needed. Clinical failure is defined as at least local failure due to newly identified extension outside of the prostate after initial regression, or urinary obstructive symptoms with carcinoma found at TURP or regional/distant failure due to radiographic evidence metastasis (nodal or hematogenous spread). Biochemical failure is defined as $PSA \geq \text{nadir} + 2 \text{ ng/mL}$
- *Failure-free Survival (FFS)*: The elapsed time from start of radiotherapy to first documented evidence of biochemical or clinical failure or death from any cause, whichever occurs first. In the absence of any event defining failure, follow-up time will be censored at the date of last documented failure-free status.

- *Overall Survival (OS)*: The elapsed time from start of radiotherapy to death from any cause. For surviving patients, follow-up will be censored at the date of last contact.
- *Biomarker expression*: Quantification of the amount of the biomarker specific immunohistochemical staining in the area of tumor
- *QOL*: Two contemporary instruments will be utilized to assess patient function and bother (Expanded Prostate Cancer Index Composite-SF12 (EPIC-SF12) and the prostate cancer-specific anxiety Memorial Anxiety Scale for Prostate Cancer patients (MAX-PC).

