12.0 CRITERIA FOR DISCONTINUATION OF THERAPY

Treatment will be stopped for grade 4 acute toxicity (according to the current version of Common Terminology Criteria for Adverse Events (CTCAE version 4), but may be resumed per protocol if the treatment break is less than 10 working days. If grade 4 toxicity resolves beyond the 10 days the treating physician will decide whether to give additional RT.

Treatment will be stopped if metastasis is detected by radiographic or pathologic evidence and the patient will be removed from the study. A work-up for metastasis during treatment will only be carried out if the treating physician deems necessary.

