14.2 Sample size, accrual rate and study duration

Study size is based on our primary objective of demonstrating that, compared to SIMRT, HTIMRT reduces the two year post treatment failure rate, by which we mean the proportion of patients with either biopsy failure or earlier evidence (within two years of treatment completion) of biochemical and/or clinical failure. (See definition in Section 9.1.) We expect the two-year failure rate in the standard fractionation arm to be 52.5%, representing the combined effect of a small rate of biochemical or clinical failure within two years, approximately 5%, and a relatively high rate of positive biopsy among the remaining 95% of patients, namely 50% ($0.05 + 0.95 \times 0.50 = 0.525$). This estimate is based on prior findings on randomized trials previously

organized by the PI. (75) Assuming equal allocation of patients to SIMRT and HTIMRT and sufficient follow-up to determine failure status at two years, a study size of 36 patients in each treatment arm provides 80% power to detect an absolute reduction of 30% in the two-year failure rate (biochemical, clinical, or biopsy), from 52.5% to 22.5%, using a one-sided Fisher's exact test with 5% significance level. To ensure a minimum of 72 study patients evaluable for the two year failure rate as our main study endpoint, we plan to enroll a total of 76 patients.

Based on an accrual rate averaging 2 patients per month, we plan to complete enrollment in 3.2 years. Patients will be followed for five years giving total study duration of 8.2 years. Analyses of some secondary endpoints, including acute toxicity, psychosocial parameters, biomarker distribution on ultrasound-guided biopsies, and initial MRI findings may be reported before the efficacy endpoints, including the primary endpoint. These secondary endpoints will be analyzed after all planned patients have been accrued, completed treatment and have a minimal potential follow-up of 3 months from the end of RT. The main efficacy endpoint requires less than five years follow up and will be performed after all patients have been assessed for two year post treatment failure status (2 yr. biopsy). Final efficacy analysis will be at the conclusion of study when patients have been followed for 5.25 years.

14.3 Definitions and endpoints:

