Evaluable: Patients who are study eligible and receive an initial dose of radiotherapy, either SIMRT or HTIMRT will be considered *evaluable for safety*, regardless of whether or not the full course of radiation treatment is completed according to protocol. To be *evaluable for efficacy*, study eligible patients must complete radiation treatment and have follow up sufficient to include either the planned 2-year post treatment biopsy or earlier evidence of biochemical or clinical failure (within 2 years of treatment completion). These patients comprise the main analysis set.

Exclusions: Any patient who is enrolled on study but does not receive an initial dose of radiation treatment will be excluded from all efficacy analyses. Any patient who initiates treatment and is later found to be ineligible for study (e.g., protocol violation) will be withdrawn from study but will be followed for toxicity and clinical outcome; the experience of such patients will be characterized separately from that of patients who are evaluable for efficacy. Reasons for exclusion of enrolled patients from analysis of safety or efficacy will be characterized.

Study endpoints are defined in Section 9.1.

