14.5 Analysis plan

The main analysis of study findings will be done by treatment assignment (intention-to-treat) in all patients who meet evaluable criteria as stated in Section 14.3. We will report any instances of treatment crossover. As noted above, analyses of some secondary endpoints, including acute toxicity, psychosocial parameters, tissue and blood product-related biomarker distribution on ultrasound-guided biopsies, and initial MRI findings may be reported before the efficacy endpoints, including the primary endpoint. These secondary endpoints will be analyzed after all planned patients have been accrued, completed treatment and have a minimal potential follow-up of 3 months from the end of RT. An initial analysis of clinical outcome (efficacy) is

planned after all patients have been assessed for two year post treatment failure status and a final analysis will be done at the completion of the planned 5 year follow up of all study patients. Statistical tests comparing treatment arms will be one-sided with 5% significance level and stratified where appropriate by the factors considered in randomization.

Statistical analysis will include descriptive statistics for patient demographics and baseline disease characteristics, both overall and by treatment arm. Counts and percentages will be used to summarize the distribution of categorical variables while median, range, mean and standard deviation will be used for continuous variables. Baseline characteristics will include age, sex, race/ethnicity, T-category, Gleason score, PSA, risk group and performance status. Biomarker measurements and proteomic/genomic profiles obtained from baseline biopsy will also be summarized with descriptive statistics. (76)

Treatment received will be summarized by the type of RT and STAD components of therapy, the number and duration of treatment delays, and the rates of discontinuation or completion. Summaries will be provided for each treatment arm. Safety analysis will include a detailed tabulation of acute and late occurring toxicity by type and grade, both overall and by treatment arm. Additionally, we will estimate the cumulative incidence (from start of treatment) of grade 2+ and 3+ genitourinary (GU) toxicity and of grade 2+ and 3+ gastrointestinal (GI) toxicity in each treatment arm. Death without the toxicity of interest will be treated as a competing risk, and toxicity rates will be compared by treatment arm using Gray's test. (77, 78)

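### The main analysis set requires completed RT, which conflicts with 4.12 for metastasis during RT, and men with neither biopsy nor failure have no sensitivity analysis

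*Combined protocol and SAP*

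**What the plan says.** Section 14.5 says the main analysis "will be done by treatment assignment (intention-to-treat) in all patients who meet evaluable criteria" in 14.3. The efficacy condition in 14.3 reads: "study eligible patients must complete radiation treatment and have follow up sufficient to include either the planned 2-year post treatment biopsy". A man without that biopsy can still qualify through a failure recorded before it, if this falls inside two years from the end of treatment. Section 14.3 calls these men the main analysis set.

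For metastasis found during RT, 4.12 stops treatment and says "the patient will be removed from the study, but not from the intent-to-treat analysis". Section 12.0 gives the same rule without the last clause: "Treatment will be stopped if metastasis is detected by radiographic or pathologic evidence and the patient will be removed from the study".

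Section 9.1 defines the two-year failure rate as a positive biopsy 2-2.5 years after RT or ADT (whichever is longer), or biochemical or clinical failure, distant failure included, "at any time prior to the planned 2 year post treatment biopsy".

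Section 8.0 and note (c) of Appendix I accept that the 2-year biopsy may be refused or contraindicated. Section 3.3.5 says patients have to know their arm. For men left out, 14.3 promises only a description of the reasons.

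**The concern.** Completing RT and having a 2-year outcome are both settled after randomisation, so the main analysis set is one of completers with an available outcome, analysed by assigned arm. Two consequences follow.

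First, the document gives opposite answers for the same man. If metastasis is found during RT, he has a recorded failure and 4.12 keeps him in the analysis, but 14.3 removes him because RT was not completed. An analyst cannot follow both sections.

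Second, a man who reaches the biopsy window without failure and is not biopsied disappears from the comparison. Because treatment is open, refusal could differ between arms and could be related to the unseen result. Nothing in the plan would show how far such men could move the one confirmatory test.

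**Working it through.** **The plan's own figure.** Inputs from 14.2: 36 evaluable per arm, failure 52.5% (SIMRT) v 22.5% (HTIMRT), one-sided Fisher's exact test at 5%. The control rate reproduces: 0.05 + 0.95 × 0.50 = 0.525. Summing over two Binomial(36) arms all tables with p ≤ 0.05 gives exact power of 80.3%, so the stated 80% is right. Expected counts are 36 × 0.525 = 18.9 and 36 × 0.225 = 8.1, that is about 19 v 8.

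**Formula.** One-sided p = hypergeometric probability of the observed number of HTIMRT failures or fewer, given the total. A restored failure adds 1 to both numerator and denominator of its arm.

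**Failures lost through the RT-completion condition**

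| SIMRT | HTIMRT | Meaning | p |
|---|---|---|---|
| 19/36 | 11/36 | largest HTIMRT count still significant against 19 | 0.047 |
| 19/36 | 12/37 | one HTIMRT failure restored | 0.064 |
| 20/37 | 12/37 | one restored in each arm | 0.0499 |
| 20/37 | 11/36 | one SIMRT failure restored | 0.036 |
| 19/36 | 8/36 | design-expected | 0.007 |
| 19/36 | 9/37 | one HTIMRT failure restored | 0.012 |
| 19/36 | 10/38 | two HTIMRT failures restored | 0.018 |

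Over all trials generated under the design rates, restoring exactly one HTIMRT failure and no SIMRT failure turns 7.6% from significant to not significant. Restoring one in each arm does so in 1.0%.

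**Men with unknown outcome.** The documents give no non-biopsy rate, so these are bounds under assumed numbers. The best case sets SIMRT unknowns to failure and HTIMRT unknowns to non-failure; the worst case is the reverse.

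| Known outcomes | Unknown per arm | Randomised | Known p | Best to worst p |
|---|---|---|---|---|
| 19/36 v 8/36 | 1 | 74 | 0.007 | 0.004-0.015 |
| 19/36 v 8/36 | 2 | 76 | 0.007 | 0.002-0.029 |
| 19/36 v 11/36 | 1 | 74 | 0.047 | 0.029-0.078 |
| 19/36 v 11/36 | 2 | 76 | 0.047 | 0.018-0.123 |
| 18/34 v 8/34 | 4 | 76 | 0.012 | 0.001-0.120 |

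The rows with 76 assume that every enrolled man is randomised. Section 3.3.5 expects withdrawal before treatment at 2-3 times 1-2%, so 2-6%: 76 × 0.02 = 1.5 to 76 × 0.06 = 4.6 men. Against that, the whole allowance for non-evaluable men is 76 − 72 = 4. The last row has 68 evaluable men, below the planned minimum of 72.

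**The case against.** The restriction is not hidden: 14.5 states it in the same sentence as the intention-to-treat label, and analysis by assigned arm is kept. A biopsy endpoint also needs a biopsy or a failure. Both points stand, but neither requires completed RT, and neither resolves the conflict with 4.12.

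Metastasis during RT should be rare. Men are screened as metastasis-free, RT lasts about 7.5-8 weeks, and work-up during RT is done only if the physician thinks it necessary. This also stands. A reader might take the 7.6% as the chance that the rule changes the trial's conclusion. It is not: it supposes that every trial loses exactly one HTIMRT failure and no SIMRT failure.

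A reader might also infer two competing definitions of the primary endpoint, because 14.2 refers to "earlier evidence (within two years of treatment completion) of biochemical and/or clinical failure" while 9.1 runs to the planned biopsy and 4.12 says "Prostate biopsies will be taken at 2-2.5 years post completion of all therapy". The documents do not support that. Section 14.2 sends the reader to 9.1 for the definition, and 14.3 says the endpoints are defined there, so 9.1 governs classification. Only the entry wording in 14.3 is loose. It matters only for a man who fails after 24 months and before a later biopsy that is then not done. Section 9.2.2 and Appendix I call for biopsy when PSA rises, so such a case should be rare.

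The separate reporting of men later found ineligible, and the exclusion of untreated men, depart from intention-to-treat but contradict no rule elsewhere. The withdrawals that 3.3.5 expects after Gleason upgrading are placed before randomisation by design.

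**Conclusion.** The point holds in two parts. Sections 4.12 and 14.3 cannot both be applied to a man whose RT is stopped for metastasis, and 12.0 leaves his place in the analysis open. The primary endpoint also has no sensitivity analysis for men with neither biopsy nor failure.

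The first part should be rare and can decide only a borderline result; a result at the design rates would survive it. The second is the larger gap. With 36 known outcomes per arm and up to 2 unknown per arm, a result at the design rates stays significant in the worst case (0.029), whereas one near the threshold does not (0.123). Only with 4 unknown per arm, which is assumed, could a result at the design rates lose significance (0.120).

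These figures show sensitivity, not bias. The documents support neither a direction nor a rate, so it would go too far to say that the plan favours HTIMRT. The sample-size arithmetic is correct. The point should be fixed but does not undermine the design.

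**What to change.** 1. In 14.3, drop RT completion as a condition for the primary analysis. Analyse eligible randomised men with a 2-year biopsy result or a recorded failure, including failure during RT, in their assigned arm. Reconcile 4.12, 12.0 and 14.3 on who is analysed; this concerns the analysis set only, not when treatment is stopped.
2. Add a best/worst-case (tipping-point) table over all randomised men, using the planned Fisher's exact test, with unknowns set to failure or non-failure in each arm. Men randomised but never irradiated and men later found ineligible enter this table with their known outcome or as unknown. The latter should not simply join the primary set: 14.3 withdraws them and follows them for toxicity and clinical outcome, with no research biopsy stated, so they might enter only by failing.
3. Keep the current evaluable set as supportive and do not call it intention-to-treat.

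Minor wording:
- Make the failure window in 14.2 and in the 14.3 entry criterion match 9.1: failure before the planned biopsy or, for men never biopsied, up to the end of the 2-2.5 year window. State that failures after a completed 2-year biopsy do not count in this endpoint; otherwise a negative biopsy followed by a PSA rise could become a failure.
- Align 1.2, 2.1 and 14.1, which name biopsy positivity or biopsy failure, with the composite primary endpoint in 14.2 and 14.5.

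The cost is revised wording and one extra table, with slight dilution from men who did not complete RT.

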Time to event endpoints will be analyzed by Kaplan-Meier (KM) or competing risk (CR) methods as indicated in the Table 14.5 (80, 77) Where the Kaplan Meier method is used, point estimates and 2-sided 95% confidence intervals will be reported for selected times such as 1, 2

and 5 years from treatment start using Greenwood's variance and the log-log transform method. Median event-free or overall survival time, if attained, will also be reported. Treatment arms will be compared by the log rank test. Cox regression models including treatment as a covariate will be used to explore the prognostic effect of baseline characteristics as well as biomarkers and proteomic and genomic profiles. Regression findings will be expressed as hazard ratios and corresponding 95% confidence intervals. For analyses involving competing risks, cumulative incidence rates will be reported for selected times with corresponding 2-sided 95% confidence intervals based on the variance estimator of Aalen and the log-log transform method. Treatment comparison of event rates will be based on Gray's test and regression models investigating prognostic factors will be fit by the method of Fine and Gray. (78, 81) Where study data indicate that at most a small number of competing risk events have occurred, analysis will be simplified by treating such events as censored observations in a Kaplan Meier analysis, since the resulting overestimation of the event rate will be negligible.

Table 14.5. Time-to-event endpoints.

Endpoint	Analysis	Events (earliest)	Competing risks	Censoring
Failure rate	CR	CF, BF, BF+ CF (within 6 months of each other) Start subsequent therapy Death related to prca without prior evidence of failure	Death unrelated to prca	Last clinical +PSA assessment
Toxicity rate (to be done separately for GI and GU)	CR	Onset of grade 2+ and 3+ toxicity	Start subsequent therapy Death, any cause	Last contact
Failure free survival (FFS)	KM	CF, BF, BF+ CF Start subsequent therapy Death, any cause	n/a	Last clinical or PSA assessment
Prostate cancer mortality	CR	Death related to prca	Death unrelated to prca	Last contact
Overall survival (OS)	KM	Death, any cause	n/a	Last contact

KM: Kaplan-Meier. **CR:** competing risk. **BF:** Biochemical failure. **CF:** clinical failure. **prca:** prostate cancer. **GI:** gastrointestinal. **GU:** genitourinary.

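### Overall survival, failure-free survival, failure rate and prostate cancer mortality have no stated analysis set except one decided more than two years after the clock starts

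*Combined protocol and SAP*

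**What the plan says.** Section 14.3 defines two sets. The safety set is eligible men who receive a first RT dose, whether or not they finish the course. To be evaluable for efficacy, an eligible man must complete RT and "have follow up sufficient to include either the planned 2-year post treatment biopsy or earlier evidence of biochemical or clinical failure"; 14.3 names this second group as the main analysis set. Section 14.5 then places the main analysis, labelled intention-to-treat, "in all patients who meet evaluable criteria as stated in Section 14.3".

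Later in 14.5: "Time to event endpoints will be analyzed by Kaplan-Meier (KM) or competing risk (CR) methods as indicated in the Table 14.5". The table lists failure rate, FFS, prostate cancer mortality and OS, plus toxicity, with events, competing risks and censoring, but no population. Section 9.1 defines OS as "The elapsed time from start of radiotherapy to death from any cause" and gives FFS the same origin. Kaplan-Meier estimates are planned at times such as 1, 2 and 5 years from treatment start. I assume the same origin for the other two endpoints, since no other is given.

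The biopsy falls 2-2.5 years after RT or androgen deprivation ends, whichever is later (9.1). Section 8.0 and note (c) of Appendix I foresee refusal and medical contraindication. No rate is given for either.

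**The concern.** Membership of the set is known only at the biopsy, more than two years after RT starts, yet OS and FFS are counted from RT start. A man cannot die failure-free before the biopsy and still belong to the set, so those years are immortal time for everyone in it who has not failed. Men who complete RT and fail early are kept, while failure-free men without a biopsy are removed, so for failure the set is selected partly on the outcome.

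This also works against Table 14.5, which counts death from any cause as an FFS and OS event and unrelated death as a competing risk. A phase III trial could report a 2-year OS near 100% simply because the deaths had been removed from the denominator.

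**Working it through.** **1. The plan's own figure.** Section 14.2 states that "a study size of 36 patients in each treatment arm provides 80% power" for 52.5% against 22.5%, with a "one-sided Fisher's exact test with 5% significance level". Exact enumeration of two binomials with 36 men per arm gives 80.28%, so the figure is reproduced. The plan enrols 76 to have 72 evaluable, an allowance of 4/76 = 5.3%. None of this changes below.

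**2. Who is in the set.**

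| History before the biopsy | In efficacy set? | Table 14.5 treatment |
|---|---|---|
| RT completed, biochemical or clinical failure | Yes | Failure and FFS event |
| Failure-free, biopsied | Yes | Followed on |
| Failure-free, unrelated death | No | FFS and OS event; competing risk for failure rate and prostate cancer mortality |
| Prostate cancer death, no earlier failure recorded | No | Event for all four |
| Subsequent therapy as only event, biopsy then not done | No | Failure and FFS event |
| Alive, failure-free, biopsy refused or missed | No | Censored |
| Metastasis during RT, RT stopped and not resumed | No (RT incomplete) | Failure and FFS event; 4.12 keeps him in the intent-to-treat analysis |

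**3. Within the plan's allowance.** Suppose all four non-evaluable men died failure-free within two years and no one died after failure. OS in all 76 is 72/76 = 94.7%; in the 72 it is 100%. Section 14.2 expects "a small rate of biochemical or clinical failure within two years, approximately 5" per cent, or 0.05 × 76 = 3.8 men. In the set this reads 3.8/72 = 5.3%, and if 25% were non-evaluable, 3.8/57 = 6.7%.

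**4. A wider range (assumptions, not in the documents).** Biopsy at T = 2.3 years from RT start; constant death hazard m = 0.005 to 0.03 per year, unrelated to failure; a fraction q = 0 to 0.25 of living failure-free men not biopsied. From the plan: 5% early failure, so λ = -ln(0.95)/2.3 = 0.0223.

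- Failed by T: F = λ/(λ+m) × (1 - e^(-(λ+m)T))
- Died failure-free by T: D = m/(λ+m) × (1 - e^(-(λ+m)T))
- Alive and failure-free: A = 1 - F - D
- Share in set: E = F + A(1-q)
- Died after failure: X = 1 - e^(-mT) - D
- In the set: OS(T) = 1 - X/E; failure = F/E; FFS(T) = A(1-q)/E; OS(5) = [F - X + A(1-q)] × e^(-m(5-T))/E

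Example, m = 0.02 and q = 0: F = 0.0489, D = 0.0438, A = 0.9073, E = 0.956. OS at T is 95.5% in all treated men and 99.9% in the set; at 5 years, 90.5% and 94.6%.

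All treated men → efficacy set, in %:

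| m | q | OS at 2.3 y | OS at 5 y | Failure at 2.3 y | FFS at 2.3 y |
|---|---|---|---|---|---|
| 0.005 | 0 | 98.9 → 100.0 | 97.5 → 98.6 | 4.97 → 5.03 | 93.9 → 95.0 |
| 0.005 | 0.25 | 98.9 → 100.0 | 97.5 → 98.6 | 4.97 → 6.59 | 93.9 → 93.4 |
| 0.03 | 0 | 93.3 → 99.8 | 86.1 → 92.1 | 4.83 → 5.17 | 88.7 → 94.8 |
| 0.03 | 0.25 | 93.3 → 99.8 | 86.1 → 92.0 | 4.83 → 6.78 | 88.7 → 93.2 |

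Five-year OS is 1.1 to 6.0 points too high. FFS runs from 6.2 points too high to 0.5 too low.

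**5. At 4% per year.** A simpler calculation compares S(5) = e^(-0.20) = 81.9% with S(5)/S(T) = e^(-0.04(5-T)), which is 88.7% at T = 2 and 90.5% at T = 2.5. The excess is 6.8 to 8.6 points.

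**6. Why the failure direction is not certain.** Step 4 omits the failure routes in table rows 4, 5 and 7. If one of the four excluded men had such an event, failure in all 76 would be (3.8 + 1)/76 = 6.3%, against 3.8/72 = 5.3% in the set.

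**The case against.** The strongest reply is that a wider time-to-event population was intended. Section 14.2 ties evaluability to the two-year failure rate. Section 14.3 expressly bars only undosed men from every efficacy analysis. It also contains two sets of evaluable criteria, and 14.5 does not say which it invokes. Competing risks and last-contact censoring suit a treated population better than a biopsy-selected one. The prognostic analysis that does condition on the biopsy says so and restarts the clock there. All this is fair and makes the intention plausible. But no such population is written, 14.3 labels the biopsy-dependent group the main analysis set, and 14.5 makes no exception.

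The size is also open to challenge. The documents give no mortality or missed-biopsy rate. At 4% per year, 76 × (1 - e^(-0.08)) = 5.8 men would die within two years, more than the plan allows for all causes of non-evaluability. These endpoints are secondary and unpowered. Those points limit the size, not the defect.

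Stronger readings are tempting but unsupported:

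- **Every finding is affected.** Section 14.5 speaks of the main analysis, and toxicity has its own set.
- **Every early failure is retained.** Incomplete RT removes a man even if he has failed, and some Table 14.5 failure events do not qualify a man for the set.
- **The treatment comparison is necessarily biased.** Similar exclusions in both arms shift both estimates without necessarily distorting the test. Nothing in the documents shows differential exclusion, although patients know their arm.

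**Conclusion.** The concern holds for the four efficacy endpoints of Table 14.5. Followed as written, the plan overstates OS whenever a man dies failure-free before his biopsy. It generally overstates cumulative failure, because most of those removed have not failed, but a few excluded failure events can reverse that. FFS bias has no fixed sign. Bias between arms requires exclusions that differ by arm.

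The 1 to 6 point excess in 5-year OS rests on 0.5-3% yearly mortality unrelated to failure and a biopsy 2.3 years after RT start; the figure of about 9 points needs 4%. The 94.7% against 100% contrast uses only the plan's allowance, but supposes that all four men died failure-free and that no one died after failure. The primary sample size is untouched. This is more than missing detail, because applying the text literally gives wrong estimates.

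**What to change.** In 14.3 and 14.5:

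- Limit the efficacy-evaluable set to the two-year failure rate and the biopsy analyses.
- Analyse failure rate, FFS, prostate cancer mortality and OS in all randomised eligible men who receive at least one RT dose, by assigned arm, from RT start, whether or not RT was completed or the biopsy done. Use the events, competing risks and censoring of Table 14.5.
- Keep 14.3's separate reporting of men later found ineligible.
- Reconcile 4.12, which keeps men stopped for metastasis in the intent-to-treat analysis, with the completed-RT condition in 14.3 and its use in 14.5.

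The cost is a few sentences. No new procedures are needed: 5.3 schedules PSA to 5.25 years and telephone follow-up of men who cannot return, and 14.5 follows progression and vital status for five years. One limit remains: examinations after about 2.25 years are at the physician's discretion (5.3), so late clinical failure may be less completely observed than PSA failure or death.
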